7.2 CONCOMITANT DISEASES AND MEDICATION

Only descriptive statistics are planned (number and percentage of patients). Summaries of concomitant diseases (medical history and baseline conditions), concomitant medication and concomitant non-drug therapy will be based on the TS, and will use actual maintenance treatment.

Baseline conditions and concomitant non-drug therapies will be coded according to the most recent version of MedDRA at the time of final DBL. This will include coding of trial-specific recording of comorbidities of obesity/overweight on the eCRF, which will not be summarised separately, but included with the general summary of medical history and baseline conditions.

Concomitant medications will be coded according to the most recent version of the World Health Organisation (WHO) Drug Dictionary at the time of final DBL.

Baseline conditions and medical history will be summarised descriptively by MedDRA system organ class (SOC) and preferred term (PT).

A medication or non-drug therapy will be considered concomitant to treatment if either of the following applies:

- It is ongoing at the start of study treatment
- The start date occurs between the start of study treatment and 28 days after the end of study treatment inclusive.

A medication or non-drug therapy will be considered prior to treatment if the end date occurs before the start of study treatment.

Concomitant medication will be summarised descriptively by ATC3 class and preferred name. Prior medication will not be summarised.

An additional table will be produced of any medications introduced on or after the date of early discontinuation of treatment, for the relevant subset of patients (regardless of whether these new medications were within or outside the 28-day period defined by the REP).

Concomitant non-drug therapy will be summarised by SOC and PT. Prior non-drug therapy will not be summarised.

7.3 TREATMENT COMPLIANCE

Treatment compliance based on return of unused and empty syringes will not be analysed in this trial.

Any discrepancies between medication assigned, medication dispensed and medication taken will be assessed through the process for determining important protocol deviations (IPDs).

[Section 6.1.3](#) and [Section 6.1.4](#) also describe situations in which the actual maintenance treatment may not be the same as the planned (randomised) maintenance treatment. The CTP specifies rules for adjusting the BI 456906 dose (or if necessary discontinuing the patient from treatment) depending on the number of missed doses and whether missed doses are consecutive. Therefore treatment compliance is directly related to the procedure for assigning BI 456906 dose.

7.4 PRIMARY ENDPOINT(S)

Descriptive summaries of body weight and percentage change from baseline will be presented over time. These summaries will be produced in each of the following different ways:

- FAS, planned maintenance treatment, all data (i.e. both on-treatment and off-treatment as defined in [Section 6.1.6](#), and irrespective of any anti-obesity medications subsequently introduced for patients who discontinued treatment early)
- FAS, planned maintenance treatment, all data (as above) but censored for any early treatment discontinuation related to the COVID-19 pandemic (either direct COVID-19 infection or other indirect pandemic-related reason)
- FAS, planned maintenance treatment, on-treatment data only
- FAS, actual maintenance treatment, all data censored for COVID-19 related treatment discontinuation
- FAS, actual maintenance treatment, on-treatment data only.

The first descriptive summary above, which uses all available body weight data, will be repeated split at each time point according to whether the contributing data are on- or off-treatment.

7.4.1 Primary analysis of the primary endpoint(s)

The primary analysis of the primary endpoint will be performed on the FAS, using planned maintenance treatment, and including all data censored for COVID-19 related early treatment discontinuation. This specifies a hypothetical estimand strategy for the intercurrent event of pandemic-related early treatment discontinuation, and a treatment policy strategy for the intercurrent event of non-pandemic-related early treatment discontinuation.

A COVID-19 related early treatment discontinuation is defined as either of the following situations):

- Direct patient COVID-19 infection: Reason for early treatment discontinuation is given on the End of Treatment eCRF page as “Adverse Event” and a treatment-emergent AE of “COVID-19” is recorded.
- Other COVID-19 restriction (site access, drug supply, quarantine, etc) which meant that study treatment could not be continued: Reason for early treatment discontinuation is given on the End of Treatment eCRF page as “Other” and the supporting comments indicate clearly “COVID-19”.

Further, “censored for” COVID-19 related treatment discontinuation is clarified to mean in practice that for patients who had a COVID-19 related treatment discontinuation (and only for these patients), only the on-treatment data will be used, as defined in [Section 6.1.6](#).

Missing data will be modelled based on what was observed up to the occurrence of these intercurrent events using direct likelihood approaches, which is a valid approach under the assumption that data are MAR.

An MMRM will be fitted to the percentage change in body weight values at each scheduled week (calculated as per [Section 6.7](#)) for this purpose. The MMRM will include fixed effects for baseline body weight as a continuous linear covariate, and treatment, gender, visit, treatment by visit interaction and baseline by visit interaction as factors. The Kenward-Roger approximation will be used to estimate the denominator degrees of freedom.

Unstructured covariance will be assumed to model the relationship between pairs of measurements taken at different weeks on the same patient. If the model fails to converge, all reasonable attempts will first be made to encourage convergence on the specified model with all scheduled weeks included. These attempts will include (but may not be limited to) first adjusting singularity options, then increasing the maximum number of convergence iterations, using the Fisher scoring algorithm for the early iterations, and providing starting values for the covariance parameters. Only if none of these options is successful will further options which simplify the fitted model be considered. In this case, reduction in the number of time points (e.g. by omitting one or more weeks during the dose escalation period) will be considered before any attempt is made to simplify covariance structure. If the latter needs to be considered as a last resort, simpler covariance structures will be evaluated in a nested sequence, where each covariance matrix is a special case of all which have been tried before.

Adjusted means will be calculated from the MMRM using the observed margins approach, in which the contribution of model factors to the estimate is weighted proportionally to the presence of these factors in the data (noting in particular that unequal proportions of males and females are expected in this trial by design).

A summary table will be produced of the MMRM results at each time point, including adjusted means and their standard errors for each treatment group, and including adjusted mean differences from placebo for each BI 456906 dose group and their 95% confidence intervals.

Adjusted means from the MMRM will also be displayed graphically over time to assess the onset of effect over time.

Adjusted means at Week 46 for each treatment group and the associated covariance matrix for those adjusted means will be extracted from the MMRM for use in the subsequent dose finding analysis using multiple comparison and modelling (MCPMod) techniques, described below:

MCPMod

The MCPMod procedure allows for simultaneous evaluation of different potential dose response patterns, whilst protecting the overall probability of Type 1 error (one-sided, 2.5%). The null hypothesis is that there is a flat dose response curve across the placebo and BI 456906 dose groups. The alternative hypothesis is that there is a non-flat dose response for at least one of the pre-specified dose response patterns specified in the CTP.

The dose response patterns were selected in the CTP to cover a plausible and diverse range of monotone patterns, and are summarised as follows:

- Linear
- Exponential: 50% of maximum effect achieved at dose 3.6 mg
- Emax1: 90% of maximum effect achieved at dose 4.8 mg
- Emax2: 70% of maximum effect achieved at dose 4.8 mg
- Sigmoid Emax: 50% of maximum effect achieved at dose 2.4 mg, 90% of maximum effect achieved at dose 4.8 mg.

The placebo mean effect was assumed in the CTP to be zero (no change in body weight from baseline). The maximum mean BI 456906 dose effect was assumed in the CTP to be -10 (percentage reduction from baseline in body weight of 10%); since only monotone shapes were considered, this is the mean effect in the highest dose group (BI 456906 4.8 mg) for all dose response patterns. It should be noted that the multiple contrast test (described below) does not use either of these two assumptions.

The multiple comparison part of the MCPMod procedure will be implemented using optimal contrast tests which control the family-wise type I error rate at a one-sided $\alpha = 0.025$. The optimal contrasts of each candidate model are calculated using weights proportional to the sample size of each dose group, which are therefore weighted equally in this trial, and these are shown in the table below:

Table 7.4.1: 1 Optimal contrast coefficients for MCPMod

Model	Contrast coefficients for treatment group				
	Placebo	BI 456906 0.6 mg	BI 456906 2.4 mg	BI 456906 3.6 mg	BI 456906 4.8 mg
Linear	0.568	0.418	-0.030	-0.329	-0.627
Exponential	0.427	0.385	0.150	-0.179	-0.784
Emax 1	0.824	0.125	-0.257	-0.327	-0.365
Emax 2	0.707	0.327	-0.199	-0.364	-0.471
Sigmoid Emax	0.521	0.507	-0.072	-0.409	-0.547

These contrasts will be updated using the expected model means for each dose group and the estimated variance-covariance matrix of the LSmeans extracted from the primary analysis model (MMRM, see above), based on the data. The updated contrast coefficients will be reported in the CTR.

Once the significance of a dose response signal is established, the dose response profile and the target dose will be estimated from the best-fitting dose response model, defined as the model with the smallest Akaike Information Criterion (AIC). The target dose for MCPMod purposes is defined as the smallest BI 456906 dose which is estimated to achieve a mean reduction in body weight of 9% more than the mean reduction obtained with placebo. If no dose within the range studied by the trial meets this criterion, then it will be concluded that MCPMod has not identified a target dose.

Estimates for each dose group will be calculated and will be based on the final dose-response model. In practice, the choice of the target dose to be investigated in Phase 3 will be based upon efficacy as well as considering tolerability and safety and other relevant information.

The results of the MCPMod analysis will be displayed in the following ways:

- A summary table will be produced containing:
 - The adjusted means from the MMRM for each dose group at Week 46 and their estimated variance
 - The updated contrast coefficients for each dose group and for each of the candidate dose response models specified above
 - The test statistics, adjusted p-values and critical values for each candidate dose response model.
- Another summary table will be produced containing:
 - The adjusted means from the MMRM for each dose group and the adjusted mean differences from placebo at Week 46
 - Predicted means for each dose group and mean differences from placebo using each of the dose response model types fitted to the data (Linear, Exponential, Emax and Sigmoid Emax)
- For each model shape, the predicted dose response curve and the 95% CI for the predicted shape will be plotted and overlaid with the adjusted means from the MMRM and their 95% CIs for each dose group at Week 46.
- For each model shape, the placebo-corrected dose response curve will be plotted and overlaid with the adjusted mean differences from placebo from the MMRM and their 95% CIs for each dose group at Week 46.

The predicted BI 456906 dose which achieved a 9% mean reduction compared with placebo will be tabulated for the significant model shapes (Linear, Exponential, Emax and Sigmoid Emax).

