3.3.4.1 Discontinuation of trial treatment

An individual patient will discontinue trial treatment if:

- The patient wants to discontinue trial treatment, without the need to justify the decision.
- The patient has repeatedly shown to be non-compliant with important trial procedures and, in the opinion of both, the investigator and sponsor representative, is not willing or able to adhere to the trial requirements in the future.
- The patient cannot tolerate the drug despite all efforts taken
- The patient requires hospitalization due to drug related gastrointestinal adverse event assessed by investigator
- The patient needs to take concomitant medication that interferes with the investigational medicinal product or other trial treatment. Refer to [section 4.2.2.1](#)

- The patient can no longer receive trial treatment for medical reasons (such as surgery, adverse events, other diseases, or pregnancy).
- Sustained symptomatic hypotension or hypertension: For hypotension, episode of symptoms (such as light-headedness or dizziness) associated with a systolic blood pressure <100 mmHg for > 60 minutes or for hypertension, episode of symptoms such as headaches, shortness of breath or nosebleeds associated with a systolic blood pressure > 160 mmHg in at least three consecutive measurements, each at least 30 minutes apart.
- Clinically relevant changes in ECG (QT prolongation >500 ms or an increase of 60 ms versus baseline, or Type Mobitz II, or third-degree AV block), or any symptomatic AV block, newly developed atrial fibrillation, or atrial flutter that require medical intervention.
- Sinus tachycardia (HR >120/min in two consecutive assessments 5 minutes apart) and/or tachyarrhythmia (HR >110/min) or cardiac conditions requiring medical intervention.
- Ventricular tachycardia in ECG or syncope.
- Clinically relevant coronary artery disease (e.g. CCS grading of Angina pectoris grade III and IV or congestive heart failure, NYHA class III-IV).
- The patient shows an elevation of AST and/or ALT ≥ 3 -fold ULN combined with an elevation of total bilirubin ≥ 2 -fold ULN (measured in the same blood sample) and/or needs to be followed up according to the 'DILI checklist' provided in the ISF.
- The patient experiences an infection with Sars-CoV-2 (as confirmed by PCR test, see [Section 5.2.3](#)) and presents with signs or symptoms requiring discontinuation of treatment as per investigator's discretion.

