PoCC will be established if at least one model is statistically significant, rejecting the null hypothesis of a flat dose response relationship for percentage change in body weight jointly over the candidate dose response models, with a contrast test controlled for the family-wise type I error rate at one sided $\alpha = 2.5\%$.

If PoCC is established, the statistically significant (best fitting) model(s) from the above candidate set will be refitted to the data to generate new estimates for all model parameters from the data. The target dose(s) will be estimated from the best fitting model(s) by incorporating information on the minimum clinically relevant effect and accounting for safety.

The primary analysis of percentage change from baseline in body weight at Week 46 will be performed using the FAS and will assign patients to the randomised maintenance dose. It will include all available data without regard to whether patients started the maintenance period

with a lower dose than the one randomised to. For patients who discontinued treatment early, a distinction will be made according to whether this is due to a COVID-19 pandemic-related reason or not. Patients who discontinued treatment early due to a pandemic-related reason (e.g. direct COVID-19 infection, drug supply issue, site closure, quarantine preventing site access) will have data handled after discontinuation as if they were missing. Patients who discontinued treatment early for any other reason will have all available data included after discontinuation, irrespective of whether such patients subsequently received any permitted anti-obesity treatments.

The above approach to the primary analysis specifies a hypothetical strategy for the intercurrent event of pandemic-related early treatment discontinuation, and a treatment policy strategy for the intercurrent event of non-pandemic-related early treatment discontinuation.

The primary endpoint will be summarised descriptively overall, and by pre-specified subgroups (to be specified in the TSAP, but which may include e.g. subgroups based on gender, baseline BMI and age at screening).

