| | | 
The interim analysis will be performed by an independent statistics and programming team within BI. Personnel involved with trial conduct at study sites will not have access to unblinded data from the interim analysis. Secure folders with restricted access will be used for the storage of unblinded interim data and results. Further operational details of who will perform the interim analysis, and the steps to be taken to protect the integrity of the ongoing trial, will be specified in a Logistics Plan. Details of the BI personnel who will have access to unblinded interim data or results, and how interim results will be communicated within BI, will be specified in an Access Plan. These documents will be finalised prior to unblinding treatments at interim database lock
 |
| Rationale for change | | An interim analysis will be performed for sponsor planning purposes only. |

11.4 GLOBAL AMENDMENT 4

| | | |
|--|--|---|
| Date of Version | | 29 Apr 2022 |
| EudraCT number | | 2020-002479-37 |
| EU number | | |
| BI Trial number | | 1404-0036 |
| BI Investigational Medicinal Product(s) | | BI 456906 |
| Title of protocol | | A Phase II, randomized, double blind, parallel group, 46 weeks dose-finding study of BI 456906 administered once weekly subcutaneously compared with placebo in patients with obesity or overweight |
| Global Amendment due to urgent safety reasons | | |
| Global Amendment | | X |

| | | |
|------------------------------|--|--|
| Section to be changed | | 3.3.4.1 Discontinuation of trial treatment |
| Description of change | | 
The patient experiences an infection with Sars-CoV-2 (as confirmed by PCR test, see Section 5.2.3).
 
Was changed to:
 
The patient experiences an infection with Sars-CoV-2 (as confirmed by PCR test) and presents with signs or symptoms requiring discontinuation of treatment as per investigator's discretion.
 |

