6.1.6 Definition of On-Treatment

It is particularly noted here that the protocol encourages continued study participation for patients who have discontinued treatment early. It is therefore expected that for some patients there will be off-treatment data captured during the planned treatment period.

In addition, even for patients who completed treatment according to the protocol, data captured during the follow-up period may be relevant for safety.

With these points in mind, it is important to be clear whether all available data will be used in a particular summary or analysis, or whether only on-treatment data will be used. The definition of “on-treatment” for this purpose is as described below. It is assumed that all patients will have

a date of last administration of study medication accurately recorded on the End of Treatment eCRF page.

“Off-treatment” refers to data which are captured after baseline but which are not “on-treatment” as defined below.

Safety

An AE start date or other safety assessment date will be considered “on-treatment” if the AE start date or assessment date is between the date of first dose and 28 days after the date of last dose of study treatment inclusive (the residual effect period (REP) is defined as 28 days in this trial).

The same on-treatment definition will be used for all types of safety data.

Efficacy

Efficacy data will also use the same 28 day definition of “on-treatment” as for safety.

The same on-treatment definition will be used for all types of efficacy data, including for all exploratory biomarkers (irrespective of whether the latter are specified as further endpoints or not).

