7.5.2 Secondary endpoint(s)

No MCPMod dose finding analyses or subgroup analyses will be performed for secondary endpoints.

Responder secondary endpoints

The analysis of responder secondary endpoints will be performed on the FAS, using planned maintenance treatment, and including all data censored for COVID-19 related early treatment discontinuation.

A frequency table will be presented of those patients achieving percentage change from baseline in body weight at each time point (up to and including Week 46) of $\leq -5\%$, $\leq -10\%$, $\leq -15\%$ and $\leq -20\%$, respectively.

The analysis of responder secondary endpoints (which are defined only at Week 46) will be aligned with the estimand strategy specified in [Section 7.4.1](#) for the primary analysis. This will be done using a multiple imputation approach on the underlying continuous body weight values, as specified below. Missing body weight measurements will be imputed using actual values of body weight, not changes from baseline. The same random seed will be used as specified for the multiple imputation sensitivity analysis of the primary endpoint in [Section 7.4.2](#).

As the first step, non-monotone (intermediate) missing values will be imputed using the MCMC method. The details of the MCMC imputation step are exactly the same as those given in [Section 7.4.2](#).

Next, the remaining monotone missing values at each week will be imputed using the sequential regression method on each of the 1000 partially imputed datasets above. The imputations will be performed using the MAR assumption, which assumes that a patient with a missing value follows a similar trajectory to a similar patient without missing data in the same treatment group (where “similar patient” means with regard to both baseline covariates and non-missing values). The order in which the imputation model is specified is important for this step, and will be as follows: treatment, gender, baseline body weight, body weight at each scheduled post-baseline week in numeric week order.

Percentage change in body weight from baseline will then be derived for each patient in each of the 1000 completely imputed datasets, and from this each of the 3 responder definitions will also be derived for each patient. In other words, the multiple imputation steps will only be performed once for all relevant responder endpoints.

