7.8.1 Adverse Events

The analyses of adverse events will be descriptive in nature. All analyses of AEs will be based on the number of patients with AEs and not on the number of AEs.

The analysis of adverse events will be based on the concept of treatment emergent adverse events. AEs will be considered “on-treatment” if the AE start date meets the 28-day REP criterion (see [Section 6.1.6](#)). AEs occurring prior to the start of treatment will be assigned to “screening”. AEs occurring more than 28 days after the last dose of study treatment will be assigned to “follow-up”. Unless otherwise specified, on-treatment AEs will be pooled across dose escalation and maintenance periods. It should also be noted that the protocol encourages continued study participation for patients who have discontinued treatment early. It is therefore expected that for some patients there will be off-treatment data captured during the planned treatment period, which will make the “follow-up” period included in AE summaries longer than the 4-week definition of scheduled “follow-up” used in the protocol, perhaps in some cases considerably longer than this.

An overall summary of adverse events will be presented for all treated patients. This summary will show the number and percent of patients with any AE, any investigator defined drug-related AE, any AE leading to the discontinuation of study medication, any AESI (as determined by the investigator), any serious AE (including reason for serious (death, life-threatening, disability/permanent damage, required or prolonged hospitalization, congenital anomaly/birth defect and other medically important events)), and any drug-related serious AE. The overall summary will be presented:

- Using actual maintenance treatment, with the treatment period pooled across, and split into, dose escalation and maintenance periods, respectively.
- Using planned maintenance treatment, with the treatment period pooled across dose escalation and maintenance periods only.

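### The SAP's rule for a direct COVID-19 discontinuation does not require COVID-19 to be the adverse event that led to stopping, so it can censor patients whose data the protocol keeps.

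*SAP*

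**What the plan says.** Protocol 7.2.2 divides early stops by cause. Weights after a stop due to a pandemic-related reason are handled as missing (hypothetical strategy). For the rest, "Patients who discontinued treatment early for any other reason will have all available data included after discontinuation" (treatment policy).

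SAP 7.4.1 restates both strategies and then gives the working definition. A stop counts as direct COVID-19 infection when the End of Treatment page gives the reason "as “Adverse Event” and a treatment-emergent AE of “COVID-19” is recorded". For patients so classed, "only the on-treatment data will be used, as defined in" SAP 6.1.6. SAP 7.5.2 carries the same censoring into the responder endpoints: "The analysis of responder secondary endpoints will be performed on the FAS, using planned maintenance treatment, and including all data censored for COVID-19".

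SAP 7.8.1 counts an adverse event as on-treatment "if the AE start date meets the 28-day REP criterion". SAP 6.1.6 sets that window as "between the date of first dose and 28 days after the date of last dose of study treatment inclusive".

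Protocol 3.3.4.1 currently makes a confirmed infection a reason to stop only if the patient also "presents with signs or symptoms requiring discontinuation of treatment", as judged by the investigator.

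**The concern.** The SAP definition joins two separate facts with an *and*: the patient stopped for some adverse event, and a COVID-19 event is on file. It does not ask whether they are the same event. A patient who stopped for, say, gastrointestinal intolerance and also had COVID-19 would be moved from treatment policy to the hypothetical strategy.

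What is lost is the off-drug weight that the protocol asks sites to make all efforts to collect, up to Week 46. The model would replace it with a missing-at-random prediction based on similar patients in the same arm. Misclassification also need not be balanced across arms, because the protocol describes gastrointestinal effects as dose dependent and intolerance leads to discontinuation.

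**Working it through.** **The wording, side by side**

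| | Protocol 7.2.2 | SAP 7.4.1, direct infection | SAP 7.4.1, other restriction |
|---|---|---|---|
| Test | Stop is due to a pandemic-related reason | Reason is an adverse event, and a COVID-19 event exists | The restriction prevented treatment, and the comments clearly say so |
| Attribution required | Yes | No | Yes |

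SAP section 4, which lists changes to the planned analysis, declares no change here. No visible SAP text supplies the link.

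**Who would be flagged wrongly**

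- *Route 1:* the patient stops for another adverse event, and COVID-19 begins within 28 days after the last dose. This is possible throughout the trial.
- *Route 2:* the patient has COVID-19, continues treatment, and later stops for another adverse event. This became mainly possible with Global Amendment 4 (version dated 29 Apr 2022). Until then the stopping criterion was simply "The patient experiences an infection with Sars-CoV-2 (as confirmed by PCR test, see Section 5.2.3"), so such a patient would normally have stopped because of COVID-19. The superseded text is used only to date this route.

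**What a flagged patient loses**

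The Week 46 target day is 323 (SAP Table 6.7: 1). Since 323 − 28 = 295, a weight taken on the target day is dropped if the last dose was before day 295.

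**Size**

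The plan gives no figure for this, and no stop, COVID-19 or retention rates or recruitment dates, so every rate below is assumed.

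- a = share of an arm stopping for a non-COVID adverse event
- c = share who would record COVID-19 over 344 days (last planned injection on day 316, plus 28)
- d = day of last dose, 71 or 141
- p = share of time on drug with route 2 open: 0, 0.5 or 1
- w = 28 + p × d, days at risk of being flagged
- r = share of flagged patients with a Week 46 weight, 0.5 to 1.0
- g = gap between modelled and observed value, 2 to 8 points

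Flagged fraction = a × [1 − (1 − c)^(w/344)]. Arm-mean shift = flagged fraction × r × g. The two adverse event processes are taken as independent.

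Central case, a = c = 0.20. For p = 0: 0.20 × [1 − 0.80^(28/344)] = 0.00360, and 70 × 0.00360 = 0.25 patients. The smallest shift is 0.00360 × 0.5 × 2 = 0.0036 and the largest is 0.00360 × 1 × 8 = 0.029. The other rows follow in the same way.

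| p | d | w | Fraction | Patients per 70 | Shift (points) |
|---|---|---|---|---|---|
| 0 | any | 28 | 0.00360 | 0.25 | 0.004–0.03 |
| 0.5 | 71 | 63.5 | 0.00807 | 0.56 | 0.008–0.06 |
| 0.5 | 141 | 98.5 | 0.01238 | 0.87 | 0.012–0.10 |
| 1 | 71 | 99 | 0.01244 | 0.87 | 0.012–0.10 |
| 1 | 141 | 169 | 0.02077 | 1.45 | 0.021–0.17 |

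With a = c from 0.10 to 0.30, route 1 alone gives 0.06 to 0.60 patients and 0.001 to 0.07 points. Route 2 open throughout gives 0.21 to 3.4 patients and 0.003 to 0.39 points.

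For scale, using the SD and arm size in protocol 7.5, the standard error of an arm mean is 7.0/√70 = 0.84 points. The largest central shifts for p = 0, 0.5 and 1 are 3%, 12% and 20% of that.

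**The case against.** The SAP states the right estimand, and the bullet is headed as direct patient infection under a definition of COVID-19 related stops. A sensible reader would take the COVID-19 event to be the one behind the stop. On this view it is a loosely worded flag and not a changed estimand. The intent may well be causal, but the text after *is defined as* is what gets programmed, and the adjacent bullet shows that the SAP states attribution where it wants it.

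The objections on size are stronger, and most of them stand:

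- Nothing changes unless the patient has a weight more than 28 days after the last dose and that value differs from the model's prediction.
- Route 2 open throughout is hard to square with the date of Amendment 4. Amendment 2 (24 Sep 2021) was already answering site queries.
- An 8-point gap is too large for most arms. Under the linear shape the assumed mean effects are 10 × 2.4/4.8 = 5 points at 2.4 mg and 10 × 3.6/4.8 = 7.5 at 3.6 mg. The protocol predicts a result comparable to placebo at 0.6 mg.
- The ranges are not bounds. A last dose on day 294 with p = 1 gives w = 322 and 0.20 × [1 − 0.80^(322/344)] = 0.0377, or 2.6 patients. A patient stopping that late has little time off drug, so a large gap is then unlikely.

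Protocol 7.1 says that no confirmatory testing is done, and SAP 7.4 presents descriptive summaries with and without COVID-19 censoring. Those summaries might reveal a material effect, but they do not correct what enters the MMRM and MCPMod. Parts of the SAP, including text in 7.9, are not public, so a supporting check elsewhere cannot be excluded. The definition in 7.4.1 itself is visible and reads as complete.

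**Conclusion.** The concern holds. Applied as written, the SAP rule censors some patients whose data protocol 7.2.2 says to keep, in the primary analysis and in the responder analyses. Confidence in the wording point is high.

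The numerical effect is probably small, and its direction depends on assumptions. With only the always-open route it is about a quarter of a patient per arm and at most 3% of a standard error in the central case. The larger figures need route 2 to be open for much of the trial, good retention and a wide gap between modelled and observed weights. The point should be fixed because an undeclared departure from the primary estimand can be removed very cheaply, not because a material bias has been shown.

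**What to change.** In SAP 7.4.1, define a direct COVID-19 discontinuation as an End of Treatment reason of adverse event together with a COVID-19 adverse event that is itself recorded as leading to discontinuation of study treatment. State that all other discontinuations for an adverse event stay under treatment policy.

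Do not add a condition that onset precedes the last dose. With weekly injections, a genuine COVID-19 stop can begin after the last injection.

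The cost is one sentence. SAP 7.8.1 already tabulates adverse events leading to treatment discontinuation, and SAP 7.9 does so for SARS-CoV-2 infection, so no new data should be needed. The change is best made before unblinding, so that no one has to decide who is censored with treatment known.
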